Official Title: Optimizing Dementia Care through Collaborative Recovery Interventions

NCT: NCT02585232

1. **Principal Investigator:** [name]
2. **All co-investigators:** [name]; [name], MA; [name], MS; [name]; [name], MEd; [name], MA; [name], BA; [name], [name], BS
3. **Consultants:** [name]; [name]; [name]; [name]
4. **Sponsor of the study or funding agency (if applicable):** VA Rehabilitation Research & Development Service (Rehab R&D) (D1824-W; Application Number: 1IK2RX001824-01A1)

5. Research setting:

This is a community-based study. All in-person study procedures will occur in a convenient community-based setting of the participant's choosing (e.g., their home, a local library, a community center, TVAMC campus, etc.). Most interactions (intervention & assessment) will occur over the telephone.

6. Purpose of the study (including hypothesis to be tested):

The purpose of this randomized controlled pilot study is to examine the preliminary effectiveness, feasibility, and potential treatment moderators (e.g., behavioral symptoms and spousal relationship status) of a newly developed intervention that combines elements of the established care consultation (CC) approach with additional counseling modules (CC+C).

Our specific aims and hypotheses follow:

Aim 1: Manualize the integration of care consultation and counseling components. The study team will begin this five-year study by refining and operationalizing the CC+C intervention. The CC+C intervention is guided by a rehabilitation and recovery-based conceptual model to address the most common high distress situations (e.g., relationship distress, veteran or caregiver depression, anxiety, or pain).

Aim 2: Evaluate preliminary effectiveness and feasibility of the CC+C Intervention. A randomized controlled pilot study of distressed dyads will be completed to compare: 1) the established CC intervention, to 2) the CC+C intervention on veteran and caregiver outcomes at 6 months.

Aim 3: Conduct exploratory analyses of the CC+C intervention on veteran long-term care placement at 6 and 12 months and examine two key treatment moderators

(behavioral symptoms and spousal relationship status) that may impact intervention engagement and response to treatment.

Hypotheses for Aims 2 and 3:

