Participants assigned to both groups will have: 1) reduced unmet needs, 2) reduced depressive symptoms, and 3) higher levels of satisfaction with care at 6 months than their baseline assessment values.

Caregivers assigned to CC+C will have greater reductions in caregiver burden at 6 months than those assigned to CC alone. Indicators of relationship strain (e.g., marital distress and/or mutuality) will show greater improvement in CC+C than CC at 6 months. 6 month gains in shared pleasant events, social engagement, and quality of life will also be greater in CC+C than in CC alone. 6-month desire to institutionalize will be lower in the CC+C group than those randomized to CC. Treatment engagement (e.g. action plan completion, attendance) is also predicted to be higher in the CC+C group than in CC.

For Aim 3, we anticipate that individuals who receive the CC+C intervention will have lower rates of placement in long-term care facilities at 6 and 12 months than those who receive CC alone. We also expect that behavioral problems will impact treatment outcomes such that those dyads with higher levels of behavioral disturbance at baseline will have greater change scores at 6 months. Spousal relationship to the veteran is also expected to moderate treatment outcome such that spousal caregivers are anticipated to have lower change scores compared to non-spousal caregivers across time; however, we expect this effect to be attenuated in the CC+C condition.

7. Background, including results of relevant research, gaps in the current knowledge.

Scope of the Problem

Over five million Americans are diagnosed with Alzheimer's disease or a related disorder (ADRD) and rates are expected to triple by 2050¹. It is the 6th leading cause of death in the United States and one in three older adults will have dementia when they die².

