10. Number of the subjects that will be recruited for study

At least seventy dyads (i.e. 70 veterans and 70 caregivers) will be recruited to achieve a final sample. However, caregivers can participate independently if the veteran is too impaired to participate meaningfully in the study.

11. Subject inclusion/selection criteria

Veterans:

- a. Must be age 19 or older
- b. Must have a diagnosis of dementia or a related disorder
- c. Must live in the community (i.e. not in a VA Community Living Center, nursing home, or other facility)
- d. Must cohabitatem with a caregiver;
- e. Must have reliable access to a telephone
- f. Must be willing to consent to participate or provide assent in conjunction with proxy consent if their decision-making capacity is compromised.

Caregivers:

- a. Must be age 19 or older
- b. Must self-identify as assisting with care for at least 8 hours/week
- c. Must be willing to consent to participate.

The study will include women and minorities and aim to represent the percentage reflected in Tuscaloosa VAMC medical care system (12% women, 44% minorities, and 1% Hispanic origin; though numbers of minorities might be slightly lower in the older cohorts targeted for this study as indicated above). No specific inclusion/exclusion criteria related to race/ethnicity are required.

12. Subject exclusion criteria

In addition to meeting the inclusion criteria outlined above, participants will be excluded in the following cases.

Veterans:

- a. Currently incarcerated
- b. Currently pregnant
- c. Dyads experiencing low levels of distress (as defined by a score of 0 or 1 on the Dementia Services Mini-Screen³², see below)

Note. Baseline or post-assessment interviews will be discontinued for Veterans experiencing severe cognitive impairment that would impair their ability to communicate during an interview, consistent with good clinical practices. However, they will not be excluded from participating in intervention sessions as appropriate and their available data (self-report or proxy report) will be retained for analyses.

Caregivers:

- a. Currently incarcerated
- b. Currently pregnant
- c. Experiencing severe cognitive impairment that would impair their ability to communicate during an interview
- d. Dyads experiencing low levels of distress (as defined by a score of 0 or 1 on the Dementia Services Mini-Screen³², see below)

13. Subject exit criteria

- a. Subjects will exit the study once one of the following conditions are met:

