17. Description of procedures to be performed.

The assessment schedule is summarized in Table 1 for screening (phone), baseline (in-person), 6-month assessment visit (in-person), and 12-month (phone) assessments. However, if a dyad prefers to complete the telephone assessments in person (e.g., while they are on station for another appointment), arrangements will be made to accommodate that request.

Table 1. Assessment Schedule

Measure (completed by Veteran or caregiver)	Admin. Time	S	B	6 mo	12 mo
Eligibility Screening (CG)	5m	X			
Dem Serv Mini-Screen (CG)	< 2m	X			
Subjective Stress/ Subjective Health (V, CG)	1m		X	X	X
Demographics (CG, CG*)	< 10m		X		
Health Literacy Screener (CG)	< 2m		X		
MoCA (V)	10m		X		

PSM IADL/ADL (CG*)	10-12m		X		
RMBPC (CG*)	5-10m		X	X	
CSDD (V, CG*)	10-20m		X	X	
Veteran QOL-AD (V, CG*)	5-10m		X	X	X
EuroQoL-5 Domain (V, CG*)	<5m		X	X	
Social Engagement (V, CG*)	<5m		X	X	
Dyadic Adj. Scale (V, CG)	5-10m		X	X	
Mutuality Scale (V, CG)	5m		X	X	X
Zarit Burden (CG)	< 5m		X	X	X
GAD-7 (CG)	< 5m		X	X	X
CES-D (CG)	5m		X	X	X
WHO-QOL-OLD (CG)	3m		X	X	
FFMQ (V, CG)	10m		X	X	X
Desire to Inst. (DTI) (CG)	<5m		X	X	X
NH Placement (EHR, CG)	<1m			X	X
Care Consultation Satisfaction Survey (CG)	<5m			X	
Caregiver Time Burden (min)			<130	<105	<50
Veteran Time Burden (min)			<80	<75	<30

Note. V = measures completed by veteran; CG = completed by caregiver; EHR = extracted from the electronic health record.

Screening

A HIPAA waiver for screening purposes will be obtained. Eligibility screening for interested dyads will typically occur over the telephone. If the Veteran and/or caregiver meets the inclusion criteria and do not meet exclusion criteria, a baseline assessment appointment will be scheduled. Informed consent procedures will be performed at baseline in accordance with the consensus recommendations for research with cognitively impaired populations developed by the Alzheimer's Association³³ and described in detail below. Proxy consent and participant assent will be collected when the participant is willing to assent for the study but is determined by the capacity assessment at the time of consent to be lacking capacity. Caregivers will also complete an informed consent. Veterans and their family caregivers will complete separate consent forms.

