r. The 6-item **Desire to Institutionalize (DTI)** Scale⁵¹, which assesses the caregivers planning, thoughts, and actions about long-term care (LTC) placement over the past 6 months will be used to assess intentions to institutionalize their loved one. Six yes/no items (e.g., taken steps toward placement) are summed for a score of 0-6. Long-term care placement and/or hospitalization of the veteran (institutionalization) will be assessed using a single item rated either by the caregiver or via electronic health record review if the dyad is no longer enrolled in the study (e.g., due to attrition).

s. The 21-item **Care Consultation Satisfaction Survey** will be used to measure the participants' satisfaction with the Care Consultant and the Care Consultation services provided.

Once baseline data are collected, dyads will be randomly assigned to a condition (see interventions delivered below).

Randomization

Blocked randomization stratified by race and gender will be used to assign participants to either the: (a) CC group, or the (b) CC+C group. This two-group experimental design was chosen over other approaches (e.g., no comparison group designs, three-group design, cross-over design, etc.) because it most closely approximates the next level of clinical research (e.g., an efficacy study), which allows for the most directly applicable conclusions.

Interventions Delivered

1. Care Consultation (CC): is an established telephone-based, empowerment intervention that uses coaching and emotional support to mobilize family caregivers and individuals with dementia through psychoeducation, resource referral, psychosocial support, and encouragement of informal and formal service use utilization. A computerized clinical tool utilizing a password-protected VA-hosted website (i.e., operated within the VA server system) called the Care Consultation Information System (CCIS) guides the care consultant through a standardized delivery of protocol components, replacing a paper-based clinicians manual. Rather than a strong focus on assessment, this intervention is designed to quickly identify areas of unmet need through brief trigger questions called the “initial assessment” – much like an interview guide – which then immediately shapes development of concrete action plans.

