The study team has extensive clinical expertise in the delivery of interventions for individuals with dementia and their caregivers. See CVs and Bios uploaded and attached to this protocol for sample publications by the study team.

20. Description of the anticipated data and how the data will be analyzed to test the specific hypotheses results.

Study Design, Power, & Target Sample Size

We plan to recruit at least 70 dyads across the 3-5 year study period to ensure 50 completers at 6 months. This rate of 2 dyads per month is feasible given that there are 421 veterans with dementia currently receiving services from the TVAMC outpatient clinics (FY2013 clinical data). If 50% of them are in moderate to high distress (a conservative estimate based on our preliminary work), there would be over 200 individuals eligible. Power analyses were conducted to support this sample size (see attached grant text for more details).

Data Management and Analysis

Data Entry:

Data will be entered using Remark Office Optical Mark Recognition software and analyzed using Statistical Package for the Social Sciences (SPSS). Data analysis will be conducted using the VA Informatics and Computing Infrastructure (VINCI) server behind the VA firewall, as has been done for other TVAMC IRB approved studies. The research assistant will review all data for accuracy and will complete data tracking forms. A descriptive analysis of all assessment data will be conducted in order to examine distributional properties and correlations between the measures and the assumptions of statistical tests will be examined. Where necessary and sensible, data transformations, including the elimination of outliers, will be considered for variables with problematic properties.

Treatment of Missing Values:

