Outcome measures for caregivers will be run in separate analyses from those of the veterans with dementia, such that a series of ANCOVAs are anticipated for 1) self-report measures for the caregiver; 2) self-report measures for the veteran with dementia; and 3) proxy-reported measures for the veteran with dementia (as rated by their caregiver). Partial eta squared statistics of effect will be used as the primary indicator of likely treatment effects in this small sample. A large effect is indicated by a partial eta squared (hp^2) greater than or equal to 0.14, a medium effect is determined by a value greater than or equal to 0.06, and small effects are determined by values greater than or equal to 0.01. For the purposes of the current study, between groups effect sizes greater than or equal to .01 (a small effect) will be interpreted as potentially clinically meaningful in the interpretation of results since two active treatments are being compared. Cohen's d statistics will also be calculated for the purposes of the current feasibility study because they are one of the most common methods of estimating effect sizes and are more easily interpreted than the partial eta squared effects. In order to calculate Cohen's d statistics, standard error terms will be converted into standard deviations and used with the estimated marginal means from the post-treatment ANCOVAs. Both types of effect sizes will be calculated. Finally, logistic regression analyses will be conducted to determine if NH placement at 6 and 12 months is differentially related to treatment condition (i.e., group assignment) for individuals with dementia. NH placement (or not) will be the dependent variable in these analyses, and independent variables will include Group and relevant covariates.

21. Risks (physical, psychological, social, and economic) and steps taken to minimize these risks.

Physical Risks: There are no anticipated physical risks with this study. All activities in the study will be within the normal limits of participants' everyday physical demands. Increased veteran activity and/or range of motion could potentially result in exacerbation

of pre-existing pain conditions (e.g., arthritis, etc.); however, potential benefits in strength/decreased disability exceed potential risks.

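### The placement outcome for Aim 3 is worded in three conflicting ways (long-term care facility, long-term care and/or hospital, nursing home), so the event in the logistic model is not determined.

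*Combined protocol and SAP*

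**What the plan says.** The placement outcome appears in four parts of the combined protocol and SAP, under three wordings.

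- **Section 6, Aim 3 and its hypothesis.** The aim is to "Conduct exploratory analyses of the CC+C intervention on veteran long-term care placement at 6 and 12 months". The hypothesis expects CC+C to show "lower rates of placement in long-term care facilities at 6 and 12 months than those who receive CC alone". No type of long-term care facility is excluded.
- **Section 17, Measures, item r.** "Long-term care placement and/or hospitalization of the veteran (institutionalization) will be assessed using a single item". The caregiver answers it, or the health record is reviewed if the dyad has left the study.
- **Section 17, Table 1.** The row reads "NH Placement (EHR, CG", with ticks at 6 and 12 months.
- **Section 20, Data Analysis.** For the logistic regressions at 6 and 12 months, "NH placement (or not) will be the dependent variable in these analyses".

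No section defines NH placement, lists the facilities that count, or says how the three wordings relate. Section 11, veteran criterion c, does separate facility types. It requires community residence, that is, "not in a VA Community Living Center, nursing home, or other facility".

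**The concern.** An endpoint should be the same event in the hypothesis, on the form and in the model. Here two groups of veterans can change status with the wording used.

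The first group moves to a Community Living Center or another residential facility that is not a nursing home. They have lost the community residence that section 11 requires at entry, and they count under the hypothesis. Taken at its word, the section 20 dependent variable leaves them out.

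The second group is admitted to hospital but not placed in long-term care. They may score on the measure r item, although the hypothesis and the model do not mention hospital stays.

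The data may not allow this to be settled later. Measure r describes a single item and no recording of facility type, so an analyst may be unable to separate nursing home, other facility and hospital. Section 32 says that the study will supply pilot data for grant proposals, and a placement rate with an unclear event is a poor basis for planning.

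**Working it through.** The documents give no placement rate, event count or power for this outcome; section 20 refers the power analysis to the grant text. There is no figure to reproduce, so the main check compares the texts.

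**Step 1: is each veteran an event?**

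| What happens to the veteran | Hypothesis (section 6) | Item r (section 17) | Model, read literally (section 20) |
|---|---|---|---|
| Moves to a nursing home | Yes | Yes | Yes |
| Moves to a Community Living Center or other long-term care facility | Yes | Yes | No |
| Hospital stay only | No | Possibly | No |
| Stays at home | No | No | No |

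The wordings agree on the first and last rows and can differ on the middle two.

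**Step 2: illustration of the facility-type gap.** Assumed inputs, none of them in the documents: 12-month long-term care placement of 20% in CC and 10% in CC+C, equal arms, and a fraction f of moves going to facilities other than nursing homes. The arm sizes are 35 (70 dyads recruited, section 20) and 25 (50 completers at 6 months, section 20).

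The nursing-home-only rate in each arm is p × (1 − f). Expected events are n × (p1 + p2), using those rates. SE(log OR) is the square root of the sum of 1/cell over the four cells.

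Example with n = 35 and f = 0: the cells are 7, 28, 3.5 and 31.5. The sum is 1/7 + 1/28 + 1/3.5 + 1/31.5 = 0.496, and its square root is 0.70.

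| f | Risk difference (points) | Events, 35 per arm | SE, 35 per arm | Events, 25 per arm | SE, 25 per arm |
|---|---|---|---|---|---|
| 0 | 10.0 | 10.5 | 0.70 | 7.5 | 0.83 |
| 25% | 7.5 | 7.9 | 0.80 | 5.6 | 0.94 |
| 33% (one third) | 6.7 | 7.0 | 0.84 | 5.0 | 0.99 |
| 50% | 5.0 | 5.3 | 0.96 | 3.75 | 1.13 |

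With the same f in both arms the risk ratio stays at 10/20 = 0.5, so the loss is in absolute difference and precision. If f differs by arm, the contrast itself moves. With f = 50% in CC and 20% in CC+C, the rates become 20% × 0.5 = 10% and 10% × 0.8 = 8%. The difference falls from 10 points to 2 and the risk ratio rises to 0.8.

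**Step 3: the hospitalization gap.** Let h be the proportion of unplaced veterans with a hospital stay, taken as equal in both arms. The combined event rate is p + (1 − p)h. The difference between arms is then (p1 − p2)(1 − h). Counting hospital stays therefore adds events and shrinks the absolute placement difference by the factor 1 − h. The documents give no value for h.

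**The case against.** The strongest reply is that NH is shorthand. The Table 1 row names the same two sources as measure r, the caregiver and the health record, and no other measure description fits that row. Measure r is worded as long-term care placement, which agrees with the hypothesis on facility type. No text uses the word only, and no coding rule exists for a move to a Community Living Center. Section 11 is an eligibility criterion, not an outcome definition.

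Much of this stands. A reader might infer that the schedule and the model count nursing homes exclusively, and that a veteran who moves elsewhere will be coded as not placed. The documents do not establish that; it is the literal reading of an undefined label.

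The reply does not settle the event, however. If NH stands for the measure r item, hospitalization comes with it, which neither the hypothesis nor section 20 includes. The item goes either to a caregiver or to a record reviewer, and without a facility list each has to decide what counts.

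A second objection is that the magnitude is wholly assumed and that the model is uninformative anyway. This also stands in large part. With 25 per arm, two-sided 5% and CC+C assumed to halve the CC rate, power is about 10% at a CC rate of 10%, 16% at 20% and 45% at 50%. The fall from 10 points to 2 needs a difference in facility mix between arms for which the documents offer no evidence. It shows sensitivity and predicts nothing.

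**Conclusion.** The inconsistency is real and concerns three wordings. Read literally, the section 20 dependent variable is narrower than the hypothesis. Read as shorthand for measure r, it may be wider, because of hospitalization. Either way the plan does not fix which event the model analyses, and the item as described may not let the intended event be recovered.

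The size cannot be derived from the documents. Under the assumed 20% versus 10% rates and 35 per arm, strict nursing-home coding would remove a quarter to a half of about 10 expected events and raise SE(log OR) from 0.70 to between 0.80 and 0.96. These figures hold only if the literal reading is the one applied.

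Importance is limited: Aim 3 is labelled exploratory, power is low at the rates assumed above, and no Aim 2 comparison depends on this outcome. The point still merits a change, because it lets the model test its own stated hypothesis at almost no cost.

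**What to change.** Use one definition in Table 1, measure r and section 20 that matches the section 6 hypothesis. Suggested wording: long-term care placement, meaning that the veteran has moved to a nursing home, a VA Community Living Center or any other residential care facility.

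On the existing item, record facility type and hospitalization as separate fields, for caregiver report and record review alike. State that hospitalization alone is not an event in the logistic model. Report nursing-home placement descriptively as a component.

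Changing only Table 1 and section 20 would leave measure r in conflict with both, so all three need the edit.

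The cost is wording in three places and a tick box on the existing item, with no added visit or participant. It should be in place before the item is administered, since facility type may be hard to reconstruct afterwards.
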